8.3.1.1 Perform 2 D echo

8.3.1.2 Prepare a heparin or citrate intravenous infusion per hospital routine to use with a standard volumetric programmable pump and Crit-Line III online hematocrit measurement device if required by the citrate protocol.

- 8.3.1.3 Assemble blood drawing supplies, including ice bucket, and label tubes.
- 8.3.1.4 Assemble and set-up Study Circuit.
- 8.3.1.5 For Subjects with AV fistula or graft, access with needles or venous cannula (i.e., angiocatheters) according to Investigator orders or per hospital routine.
- 8.3.1.6 For Subjects with tunneled catheters, aspirate heparin flush according to Investigator orders or per hospital routine.
- 8.3.1.7 Review medical history.
- 8.3.1.8 Review concomitant medications.
- 8.3.1.9 Obtain BP, RR, and HR, weight without shoes or over clothes, and oral temperature. Perform physical exam.
- 8.3.1.10 Obtain blood for albumin according to instructions in **Appendix 2**.
- 8.3.1.11 Obtain blood for basic metabolic panel according to instructions in **Appendix 2**.
- 8.3.1.12 Obtain blood for CBC with differential and platelets according to instructions in **Appendix 2**.
- 8.3.1.13 Obtain blood for systemic soluble markers according to instructions in **Appendix 2**.
- 8.3.1.14 Obtain blood for flow cytometry according to instructions in **Appendix 2**.

Initiate the Study Hemodialysis Treatment (SHH or SCD Treatment)

- 8.3.1.15 Begin intravenous heparin infusion as prescribed by standard protocol (*for SHH treatment, heparin will be used for the entire duration of the procedure. For the SCD treatment, heparin will be used only during the first hour of the SCD treatment.*)
- 8.3.1.16 Turn on blood pump at the speed prescribed by the Principal Investigator. Turn on the calcium infusion per protocol.
- 8.3.1.17 Obtain BP, HR, and RR.

Repeated Procedures During Entire Study Hemodialysis Treatment (SHH or SCD Treatment)

- 8.3.1.18 Record Adverse Events.
- 8.3.1.19 Record concomitant medications.
- 8.3.1.20 Adjust heparin flow rate as needed for SHH or calcium chloride administration rate for SCD treatment protocol to maintain systemic iCa level between 1-1.3 mM during the citrate anticoagulant therapy. Document the pre-SCD filter ionized Ca as required.
- 8.3.1.21 Observe cartridges for evidence of hemolysis, clotting, and leakage hourly.

At 1 Hour into Study Treatment Protocol (For SCD Treatment Only)

- 8.3.1.22 Obtain blood for iCa with i-STAT, a bedside diagnostic device (Abbott Labs).
- 8.3.1.23 At 1 hour, stop heparin, change dialysate to zero calcium and start citrate and calcium infusion. After 3 minutes of citrate and calcium infusion, stop the blood pump, clamp the venous return line. Please refer to Fresenius Operator's Manual on how to integrate the SCD to circuit. Within the first 10 minutes of initiating citrate with the integrated *SCD* obtain blood from sampling port of arterial segment of extracorporeal circuit (pre-citrate infusion) and send for iCa using a bedside i-STAT Analyzer (**Appendix 2**).

At 2 Hour Into Study Treatment (For SCD Treatment Only)

- 8.3.1.24 For *SCD treatment protocol*, obtain blood for iCa from extracorporeal blood circuit (pre-citrate infusion) arm using the bedside i-STAT Analyzer.

At 3 Hours Into Study Treatment (For SCD Treatment Only)

- 8.3.1.25 For *SCD treatment protocol*, obtain blood for iCa from extracorporeal blood circuit (pre-citrate infusion) using the bedside i-STAT Analyzer.

At 4 Hours Into Study Treatment (For SCD Treatment Only)

8.3.1.26 For *SCD treatment protocol*, obtain blood for iCa from extracorporeal blood circuit (pre-citrate infusion) using a bedside i-STAT Analyzer.

At 5 Hours Into Study Treatment (SHH and SCD Treatment except if indicated otherwise)

8.3.1.27 Obtain blood for basic metabolic panel according to instructions in **Appendix 2**.

8.3.1.28 Obtain blood for CBC with differential and platelets according to instructions in **Appendix 2**.

8.3.1.29 Obtain blood for systemic soluble markers according to instructions in **Appendix 2**.

8.3.1.30 Obtain blood for flow cytometry according to instructions in **Appendix 2**.

8.3.1.31 For *SCD treatment protocol*, obtain blood for iCa with i-STAT Analyzer.

End the Study Treatment Period

8.3.1.32 Discontinue heparin infusion in heparin anticoagulant treatment or citrate infusion in citrate anticoagulant treatment.

8.3.1.33 Remove any peripheral intravenous catheter(s).

8.3.1.34 For Subjects with AV fistula or graft, remove needles or venous cannula (i.e. angi catheters) and obtain hemostasis according to Investigator orders or per hospital routine.

8.3.1.35 For Subjects with tunneled catheters, disconnect tubing and instill heparin flush according to Investigator orders or per hospital routine.

8.3.1.36 Obtain oral temperature, BP, pulse, and weight without shoes or overclothes.

8.3.1.37 Disassemble the Study Circuit.

8.3.1.38 Perform 2 D echo

8.3.1.39 The Subject may be discharged after at least 1 hour of observation following completion of his/her last study treatment. At the Investigator's discretion, the Subject may be kept for observation beyond 1 hours, if needed. During this 1 hour observation period, additional iCa may be obtained post SCD treatment session, upon PI's determination.

24 hours after Treatment (SHH or SCD Treatment)

8.3.1.40 Perform 2 D echo

8.3.1.41 Obtain blood for systemic soluble markers according to instructions in **Appendix 2**.

8.3.1.42 Obtain blood for flow cytometry according to instructions in **Appendix 2**.

Before Initiation of SCD Treatment

8.3.1.43 The PI must review all safety data of the Subject and determine their suitability to move to the SCD treatment. Further, the WBC count must be $>4000/\text{mm}^3$, neutrophil count >500 and platelet count $>50,000/\text{mm}^3$ in prior treatments.

Ionized calcium during SCD Treatment

8.3.1.44 The PI may draw more frequent iCa using i-STAT device if deemed necessary for safety concerns.

8.4 Detailed Study Measures

8.4.1 Echocardiographic Methods

Complete transthoracic echocardiograms including structural imaging, color Doppler for evaluation of valvular regurgitation, spectral Doppler for hemodynamic quantitation and longitudinal strain in 3 views for calculation of global longitudinal strain (GLS) will be performed at each time point as per the specified protocol.

All echocardiograms will be performed on an identical echocardiographic platform (Epiq, Philips Ultrasound, Andover MA) using identical platform upgrades and software. Standard measures of left ventricular dimensions and volume from which ejection fraction will be calculated will be

performed off-line using the digitized images. The calculation of GLS will be performed using the integrated software of the platform.

Specific echocardiographic parameters to be quantified at each time point are as noted on the echocardiographic case report form.

Because the majority of echocardiographic parameters which reflect left ventricular contractility are both pre-and afterload dependent a substantial range of findings across patients is unavoidable and it is not feasible within the scope of a study this size to identify “normative” values nor is it possible to accurately identify thresholds of change in parameters such as ventricular size or ejection fraction in patients in whom intravascular volume and systemic systolic pressures vary. Each patient will therefore serve as his or her own control comparing pre-and post-dialysis echocardiograms following standard dialysis compared to pre-and post-echocardiograms following investigational dialysis using the SCD device^{36,37}.

Assessment: Echocardiographic parameters which are less (but not entirely) preload and afterload dependent include quantitation of regional wall motion abnormalities as well as calculation of GLS. Normative values for regional wall motion abnormalities are defined as normal thickening and endocardial excursion in all regions and any deviation from normal thickening or excursion is considered abnormal. Regional wall motion will be scored using a standard wall motion scoring scheme. (1=normal; 2=hypokinetic; 3= akinetic; 4=dyskinetic). Scores will be tabulated for each of 16 predefined segments and a global wall motion score calculated as the sum of individual scores divided by the number visualized segments. For this scheme a score of 1 represents normal ventricular function with progressively higher numbers representing progressively worse systolic function. Scores from pre HD, post HD and 24 hour post HD Echos from all 10 patients will be collated and analyzed for statistical significance between Treatment 1 and Treatment 2 groups.

Global longitudinal strain will be obtained using tissue tracking methodology³⁸. There is a significant range within the left ventricle of normal values for regional strain depending on wall location. Values for normal GLS in normal controls have ranged from -16.0 to -22.0. Patients with systemic diseases including hypertension, diabetes and renal disease have all been described to have reduced GLS in the absence of overt systolic dysfunction. As “normal” values for GLS cannot be predicted in the patient population under consideration each patient will serve as his or her own control for tracking improvement or deterioration in global longitudinal strain.

Assessment: The largest body of data regarding using global longitudinal strain for tracking myocardial performance is in the patients receiving cardiotoxic chemotherapeutic agents where a threshold of 10-15% change has been considered as significant variation from baseline³⁹. This will be used as a dichotomous threshold for defining either improvement or deterioration in GLS.

Echocardiographic images will be interpreted at the Echo Laboratory, Frankel Cardiovascular Center, Floor 3. Area B, University of Michigan, Ann Arbor, MI

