The mortality rate in ESRD patients requiring chronic hemodialysis treatment is unacceptably high with almost half of the deaths due to cardiovascular disease (CVD). This excessive CVD mortality is not due to classical atherosclerotic disease complications but mainly due to cardiac failure and sudden death, often during the dialysis procedure^{1,2}. The pathogenesis of heart failure in this patient population appears to be due to intradialytic recurrent myocardial stunning (MS) as defined as ischemia mediated transient reduction in myocardial function. Overtime these recurrent ischemic insults results in irreversible fibrotic changes, chronic heart failure, arrhythmias, and sudden cardiac death^{3,30,31}. In this regard, hemodialysis-induced myocardial ischemia and MS has been found to be common in these patients and is significantly associated with high rates of ultrafiltration and intradialytic hypotension⁴. Of note, pediatric patients devoid of atherosclerotic coronary artery disease also have had a high incidence of MS³². MS in HD patients promotes both ischemia induced areas of hypokinesis and akinesis. The majority of these areas of MS improve within 30 minutes post hemodialysis^{33,34}. More frequent HD regimes are associated with lower UF volumes and reduction of intradialytic hypotension and MS events. This relationship may explain in part improved outcomes associated with more frequent HD, such as nocturnal or home HD, compared to the conventional 3 times a week HD treatment program³⁵. MS may be the critical pathophysiologic factor promoting the CV related deaths predominated by heart failure and sudden death in ESRD patients on chronic hemodialysis.

Immunomodulatory Biomimetic Device to Treat Myocardial Stunning in ESRD Patients

This clinical protocol will evaluate the influence of the SCD on myocardial stunning events in ESRD patients in chronic hemodialysis patients. Regional citrate anticoagulation

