8.5 Study Exit Procedures

A Study Termination form will be completed for all patients who have completed the Study Procedures according to the protocol as well as for those who are terminating early for any cause

9. Statistical Considerations

Sample size determination for primary outcome regional wall abnormalities: Our consultant, [name] has previously demonstrated a difference in this variable in 8 to 10 patients using a similar protocol to this proposal when comparing standard and biofeedback dialysis and dialysis cooling ^{33,34}. Sample size of 10 would appear to be sufficient to detect a difference of 20% and is based upon a standard deviation of 14%, significance level of 0.05 and 80% power. In the [name] studies, differences of greater than 20% were observed. We plan to recruit 10 patients in this study, to better ensure an adequate sample size to obtain statistically relevant primary and secondary endpoint comparisons. The patients will serve as their own controls, comparing BL-SHH parameters to SCD therapy parameters. Independent t-test will be used to compare the peak frequency of MS between SHH and SCD sessions. Global LVEF and wall motion in 16 segments in 8 regions at each time point in the dialysis session will be compared using repeated measures and Bonferroni's test for multiple comparisons. IDWG will be compared using paired and unpaired non-parametric testing or t-test if the variable is

normally distributed. These approaches have shown significance in prior studies for MS in HD. Statistical correlations are planned for regional wall abnormalities, inflammatory indices, monocyte subsets and pre-dialysis blood pressures ^{33,34}

10. Adverse Events

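### The wall-motion tests in 8.4.1 and section 9 do not carry through the pre-to-post comparison that 8.4.1 itself sets out

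*Combined protocol and SAP*

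**What the plan says.** Section 9 names regional wall abnormalities as the primary outcome. Four statements bear on how wall motion is compared.

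- Section 8.4.1, general paragraph, which sets a within-patient comparison: "comparing pre-and post-dialysis echocardiograms following standard dialysis compared to pre-and post-echocardiograms following investigational dialysis using the SCD device". This is a difference between two within-session changes. No test is named, and the 24-hour scan is not mentioned.
- Section 8.4.1, wall-motion assessment, where the two treatments are the groups compared: "Scores from pre HD, post HD and 24 hour post HD Echos from all 10 patients will be collated and analyzed for statistical significance". No test, contrast, baseline or primary time point is given.
- Section 9, which adds a Bonferroni correction: "Global LVEF and wall motion in 16 segments in 8 regions at each time point in the dialysis session will be compared using repeated measures". There is no baseline term.
- Section 9, on a different summary: "Independent t-test will be used to compare the peak frequency of MS between SHH and SCD sessions". Again there is no baseline term.

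For the soluble markers, by contrast, section 8.4.2 states outright that the patient's pre-treatment value is the baseline.

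**The concern.** The pre-dialysis scan in the SCD session is taken before any exposure to the device (8.3.1, Appendix 1), so it can carry information about starting function but no SCD effect. The wall-motion tests nevertheless list it beside the outcome scans. Two consequences follow.

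First, Treatment 2 always comes one week after Treatment 1 (8.3.1). If patients start the second session with better or worse wall motion, a raw comparison of post-dialysis scores carries part of that difference into the apparent SCD effect. Section 8.4.1 itself accepts that wall motion is not fully independent of loading conditions.

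Second, a Bonferroni correction that counts the pre-dialysis scan makes the test at the informative scan stricter for no gain.

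With 10 patients and several admissible analyses of the primary outcome, the choice of contrast could also be made after the data are seen.

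**Working it through.** **Inputs.** From section 9: n = 10, difference 20%, SD 14%, significance level 0.05, power 80%. Assumptions: two-sided test; r, the correlation between the pre-dialysis and post-dialysis SCD-minus-SHH differences, from 0 to 0.7 (not given in the plan). All powers use the noncentral t distribution.

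**1. The plan's own sample size.** Section 9 does not say whether 14% is the SD of one session or of the paired difference.
- Per-session SD, zero correlation between sessions: SD of differences = 14 × √2 = 19.8. Noncentrality = 20 / (19.8/√10) = 3.19 and power = 81%, so n = 10 is reproduced.
- SD of differences = 14: noncentrality = 20 / (14/√10) = 4.52. Power is 98% at n = 10; n = 7 would give 88%.
- Two independent groups, SD 14: 81% with 9 per group, 86% with 10.

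Both paired readings are carried forward.

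**2. Raw post-dialysis comparison.** At 0.05 the power is 98% (SD 14) or 81% (SD 19.8). With Bonferroni over three scans (0.05/3 = 0.0167) it is 91% or 61%. The plan does not state the divisor. If only the two scans on the dialysis day count (0.025), it is 95% or 69%.

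**3. Post-dialysis difference adjusted for the pre-dialysis difference.** Residual SD = SD × √(1 − r²), with one degree of freedom lost (computed as n = 9), tested at 0.05.

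**4. Simple change score.** SD = SD × √(2(1 − r)), n = 10, tested at 0.05.

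| r | Adjusted, SD 14 | Adjusted, SD 19.8 | Change, SD 14 | Change, SD 19.8 |
|---|---|---|---|---|
| 0 | 96% | 76% | 81% | 52% |
| 0.3 | 97% | 79% | 92% | 67% |
| 0.5 | 99% | 86% | 98% | 81% |
| 0.7 | 99.9% | 96% | 99.9% | 96% |

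Against a raw post-dialysis test at 0.05, adjustment costs a little at r = 0 (96% against 98%; 76% against 81%) and gains at r = 0.5 (99% against 98%; 86% against 81%). At low r, the advantage over step 2 therefore comes from naming one contrast rather than from the covariate.

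**5. Starting difference.** If the pre-dialysis differences have the same SD, chance alone gives their mean a standard error of 14/√10 = 4.4 or 19.8/√10 = 6.3 percentage points. A raw post-dialysis comparison carries r times the starting difference. At r = 0.5, a one-standard-error imbalance puts 2.2 or 3.1 points into the estimate. Adjustment removes that part.

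**6. What averaging the three scans would do.** If a fraction f of the effect persists at 24 hours, the averaged effect is 20(1 + f)/3: 6.7 for f = 0, 10 for f = 0.5, 13.3 for f = 1. With an SD of differences of 14 at each scan, the SD of the average is 14 × √((1 + 2r)/3). Power from r = 0 to r = 0.7 falls from 64% to 33% (f = 0), 93% to 61% (f = 0.5) and 99.6% to 85% (f = 1).

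**The case against.** The strongest reply is that the plan already contains the right comparison. The general paragraph of 8.4.1 sets it out, the wall-motion sentence sits under it, and a repeated-measures layout that includes the pre-dialysis scan can supply a treatment-by-time term. This stands as evidence of intent. It does not settle the test: no section names that term, and section 9 describes comparisons at each time point.

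A reader might infer that the plan pools the three scans and so shrinks a real effect to a third. The documents do not support this. Collating scores is assembling them, no average is specified, and a comparison at each time point leaves a post-dialysis effect at its full 20%. The one-third figure also needs no effect at 24 hours. Section 1 does say "The majority of these areas of MS improve within 30 minutes post hemodialysis", but it also reports improved myocardial performance lasting up to 4 weeks in a canine heart-failure model, and a monocyte shift lasting up to 2 weeks in diabetic dialysis patients. Those are different settings, but they leave a 24-hour effect open. With full persistence and low correlation, averaging would be more powerful than a change score (99.6% against 81% at r = 0, SD 14).

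A reader might also infer that the plan ignores the pre-dialysis score. It does not: 8.4.1 uses it in principle. What is missing is the step from principle to test.

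Finally, this is a small exploratory trial, and the synopsis calls its primary analyses descriptive. But section 9 sizes the trial for a significance test of this outcome, so the contrast needs defining.

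**Conclusion.** The point holds in a limited form: the plan states a baseline-referenced echo comparison and then specifies wall-motion tests without a baseline term, counting a pre-exposure scan among the compared time points. On the plan's 20% difference with 10 patients, one adjusted post-dialysis contrast has 96 to 99.9% power (SD of differences 14) or 76 to 96% (19.8), against 91% or 61% for the raw post-dialysis comparison with Bonferroni over three scans. A starting difference between sessions would also no longer pass unadjusted into the estimate.

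These sizes rest on a two-sided test, r from 0 to 0.7, a Bonferroni divisor of three, and an unresolved meaning of the 14%. They are on the percent scale of section 9; the plan gives no SD for the 1-to-4 wall-motion score. Dilution to one third is a property of averaging with no 24-hour effect (one half to two thirds if half to all of the effect persists), not of the plan as written.

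**What to change.** In 8.4.1 and section 9, define the primary wall-motion contrast in the same words: the within-patient SCD-minus-SHH difference in the post-dialysis score, adjusted for the difference in the two own-session pre-dialysis scores. Use the pre-dialysis scans only as baseline, and report the 24-hour scan as a separate secondary contrast. State which SD the 14% is.

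Covariate adjustment is preferable to a simple change score as the primary analysis because the change score loses much power at low correlation. The change score is worth reporting as a sensitivity analysis, since it subtracts the whole starting difference rather than the predicted part.

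The cost is wording and one degree of freedom at n = 10. No new data are needed: the pre-dialysis echo is already scheduled in both sessions. Adjustment does not remove an order effect that arises during the session, so the fixed sequence remains a limitation to state.

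### The only stated decision rule for strain is a cut on whole-ventricle GLS, under which stunning confined to a few segments can be classed as no change

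*Combined protocol and SAP*

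**What the plan says.** The background (Section 1, on myocardial stunning in ESRD) describes the target event as regional: "MS in HD patients promotes both ischemia induced areas of hypokinesis and akinesis".

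Section 8.4.1 specifies "longitudinal strain in 3 views for calculation of global longitudinal strain (GLS) will be performed at each time point". Its reason for not relying on norms is that "There is a significant range within the left ventricle of normal values for regional strain depending on wall location", so each patient serves as his or her own control. The cut comes from "patients receiving cardiotoxic chemotherapeutic agents where a threshold of 10-15% change has been considered as significant variation from baseline". The section then states: "This will be used as a dichotomous threshold for defining either improvement or deterioration in GLS".

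No segmental strain measure is stated, and Section 9 names no test for strain. The synopsis lists myocardial strain as a key measurement and includes it in the descriptive primary analyses. The full list of echocardiographic parameters is left to a case report form that is not in the documents.

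Wall motion is handled separately and by segment: "Scores will be tabulated for each of 16 predefined segments", on the scale "1=normal; 2=hypokinetic; 3= akinetic; 4=dyskinetic". Section 9 names regional wall abnormalities as the primary outcome.

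**The concern.** GLS summarises the whole ventricle. A loss confined to a few segments is diluted by the segments that still contract normally, so a focal event can leave GLS inside the cut. No single value between 10% and 15% cures this, so the point is separate from the choice of value.

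The cut also comes from a different clinical setting. Section 8.4.1 says that thresholds of change cannot be accurately identified for ventricular size or ejection fraction in these patients because loading varies. It calls GLS less, but not entirely, load dependent, and still adopts a fixed threshold for it.

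The variation of normal strain by wall limits comparison with reference values. It does not prevent comparing the same segment of the same patient before and after dialysis, which is the kind of comparison the section adopts.

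At stake is the reading of the strain result. A session with focal stunning may be recorded as showing no deterioration, and few differences between SCD and heparin sessions would then show on that classification.

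**Working it through.** **The plan's own figure.** Section 9 gives 10 patients for a 20% difference, SD 14%, significance level 0.05 and 80% power. The two-sided two-sample normal formula gives 2 × (1.96 + 0.84)² × 14² / 20² = 7.7, so 8 per condition, with power 89% at 10. A paired t-test with 10 patients has power 97.9% if 14% is the SD of the differences, and 81.1% if that SD is 14 × √2. Ten is therefore sufficient on these variants. That calculation concerns regional wall abnormalities; the plan gives none for strain.

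**Inputs for the GLS check.**
- Cut: 10-15%, read as a relative change (8.4.1). Read as absolute strain points it would be far harder to reach, since "Values for normal GLS in normal controls have ranged from -16.0 to -22.0".
- Segments: 16, stated for wall motion and assumed for GLS; 17 and 18 also tried.
- Weights: equal, with equal baseline strain (assumed; the plan gives none).

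**Formula.** If k of S segments each lose a fraction f of their strain, and their baseline strain is w times the average, the relative change in GLS is k × f × w / S.

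**Results with w = 1.**

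| Pattern | S = 16 | S = 17 | S = 18 |
|---|---|---|---|
| 1 segment, all strain lost | 6.25% | 5.9% | 5.6% |
| 3 segments, half lost | 9.4% | 8.8% | 8.3% |
| 2 segments all lost, or 4 half lost | 12.5% | 11.8% | 11.1% |

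At GLS -16 to -22 with 16 segments, the first row is 1.0 to 1.4 strain points and the second 1.5 to 2.1. The third row falls inside the 10-15% band, where the plan defines no class. Reaching 15% takes five segments losing half (5 × 0.5 / 16 = 15.6%) or eight losing 30% (8 × 0.3 / 16 = 15.0%).

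**Robustness.**
- Single akinetic segment: reaching 10% with 16 segments needs w = 10 / 6.25 = 1.60. It stays below 10% down to 11 tracked segments (1/11 = 9.1%).
- Three half-lost segments: reaching 10% needs only w = 10 / 9.375 = 1.07. With 15 tracked segments the change is 1.5/15 = 10.0%, and with 14 it is 10.7%. Against a 15% cut, w would have to be 1.60.

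**Illustrative simulation, all inputs assumed.** Ten patients; on average 3 stunned segments with heparin and 1 with SCD; each loses 50% from a baseline of 16 points; segment noise SD 2-4 points; shared noise SD 0.5-1 point. Exact McNemar test for the dichotomy, paired t-test otherwise. Ranges are over all settings tried, including some with the noise added to every scan.
- Heparin sessions flagged: 44-48% at the 10% cut, 10-33% at the 15% cut.
- Power: 4-16% for the 10% dichotomy, at most 2% for the 15% dichotomy, 15-80% for continuous GLS, 20-98% for a sum of same-segment losses.

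**The case against.** Much of the opposing case stands.

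- **Regional events are recorded elsewhere.** One akinetic segment moves the mean wall-motion score from 1.000 to (15 + 3)/16 = 1.125; three hypokinetic segments move it to (13 + 6)/16 = 1.1875. Any deviation from normal counts as abnormal. A reader might infer that the trial cannot see focal stunning. The documents do not support that.
- **The GLS cut may not be the only strain summary.** The synopsis plans a descriptive analysis of strain, and the case report form could already list segmental values. What can be said is that the cut is the only decision rule stated.
- **The arithmetic rests on equal weights.** Section 8.4.1 itself says strain differs by wall, and the three-segment example reverses under small departures. The single-segment example does not.
- **A segmental sum is not always better.** The simulated scenario is focal, which favours it. With an assumed diffuse 1-point SCD gain and no focal stunning, continuous GLS had more power in all six settings tried (for example 80% against 70%, and 60% against 47%).
- **A sum of losses turns noise into apparent stunning.** With an assumed 25% more segment noise in one session, its false-positive rate was about 6-14%, while GLS stayed at 5-6%. Treatment order is fixed, so session differences are not balanced.
- **Much of the power loss comes from dichotomising**, not from using a global measure. That supports analysing GLS as continuous.

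The trial is also a 10-patient exploratory pilot, which limits how much the point should weigh.

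**Conclusion.** The point holds for the strain outcome alone. The stated rule for strain is a dichotomous cut on a whole-ventricle average, taken from another population, while the event of interest is regional. With 16 equally weighted segments of equal baseline strain, one fully akinetic segment (6.25%) falls clearly below the cut. Three half-lost segments (9.4%) fall just below 10% and well below 15%. Both can be classed as no change; neither must be in every patient.

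A reader might infer that stunned sessions would usually be missed. The illustrative figures do not show this at the 10% cut, where flagging is close to an even chance; misses are the clear majority only at 15%. All flagging and power figures rest on assumed stunning and noise values and should not be read as the trial's operating characteristics.

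This is an inexpensive improvement to a key measurement. It does not undermine the primary outcome.

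**What to change.** In Sections 8.4.1 and 9:

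1. Compare the pre-to-post change in GLS between the SCD and heparin sessions within patient, as a continuous measure. Keep the cut only as a descriptive class.
2. Beside it, as a supportive analysis, report a same-segment strain summary from the 3 views already acquired, using only segments tracked in both scans (pre and post) of both sessions. Report gains as well as losses, and the number of tracked segments per session.
3. State that a GLS change below the cut does not show absence of stunning.

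The cost is protocol and SAP wording plus export of segmental values, with no new scan. This assumes that the strain software provides those values, which the plan does not say. The downsides are that segmental strain is noisier than GLS, some segments will not track, and a losses-only sum rises with measurement noise and has less power than GLS for a diffuse effect. The segmental summary should therefore support GLS, not replace it.
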